7.3 Duration of the Study and Patient Participation

Patient enrollment is expected to be completed within 1 year of study initiation. Total study duration (from study initiation through patient enrollment and follow-up) is expected to be 15 months.

A review of the patient's medical chart through 90 days after the study procedure will be conducted.

7.4 Measures to be Taken to Avoid or Minimize Bias

This study is designed as a stratified, randomized, controlled clinical trial to minimize bias in both assigning patients to treatments and in analyzing the results. Each clinical site is limited to a maximum number of patients (as described in Section 11.1: Sample Size) to minimize bias that may be introduced if the majority of patients are enrolled at

one or two clinical sites. In addition, the study will utilize uniform definitions for study endpoints.

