7.4.1 Randomization

Once baseline angiography is complete and patient eligibility is confirmed, patients will be randomized into either the Enforcer balloon or conventional angioplasty group prior to treatment. At each study site, patients will be stratified for randomization based on the number of lesions requiring treatment (single lesion or two lesions) and type of AV access circuit (fistula or graft), then randomized to one of the treatment groups in a 1:1 ratio.

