11.0 Statistical Considerations

11.1 Sample Size

The expected rates of adjunctive therapy for the Enforcer balloon and conventional angioplasty groups were assumed to be 5% and 15%, respectively. A sample size of at least 250 total lesions (125 lesions per group) is required to detect a 10% difference in the rate of adjunctive therapy with a power of 80% and a type I error of 0.05. Prior experience suggests that 40% of patients, on average, would also have a second lesion treated. Therefore the study will enroll approximately 200 patients (approximately 100 patients per group) and enrollment will continue until at least 250 lesions are treated. Procedural outcomes are unlikely to depend on the connectivity between lesions within an AV dialysis access circuit or the patient-level factors which affect longer-term outcomes, and therefore lesions were assumed to be independent for the purposes of the sample size calculation.

Up to 10 clinical sites will be included in the study, and the maximum enrollment per clinical site will be no more than 80 patients or 40% of the total enrollment. There is no minimum enrollment threshold. Patients that withdraw from the study will not be replaced.

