11.5 Site-level Poolability

This is a multi-center study with up to 10 clinical sites. It is not intended to incorporate study sites into primary endpoint analyses. However, the primary endpoint will be examined across sites and reported if necessary.

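### The per-site cap rules out a one-site majority but not the two-site majority that Section 7.4 names; site, a randomisation factor, is also left out of the primary analysis

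*Combined protocol and SAP*

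**What the plan says.** Section 7.4 lists a per-site maximum among the measures against bias. Its purpose is "to minimize bias that may be introduced if the majority of patients are enrolled at" "one or two clinical sites", and the reader is sent to Section 11.1 for the figure.

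Section 11.1 gives it: "the maximum enrollment per clinical site will be no more than 80 patients or 40% of the total enrollment". The same section plans about 200 patients, with enrolment continuing until at least 250 lesions are treated. On sites it says "Up to 10 clinical sites will be included in the study". No minimum number of sites is stated, and a minimum enrolment is expressly ruled out.

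Site is part of the allocation scheme. Section 7.4.1 says "At each study site, patients will be stratified for randomization", by number of lesions and type of access circuit, and Section 11.2 repeats that the 1:1 ratio applies at each site.

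On the analysis, Section 11.3.1 specifies a one-sided Z-test on the two rates, with adjusted differences reported only if an adjustment is applied. Section 11.5 says "It is not intended to incorporate study sites into primary endpoint analyses". It adds that the endpoint will be examined across sites, but makes reporting conditional on need and gives no method or criterion.

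**The concern.** The purpose in Section 7.4 covers two situations: a majority at one site and a majority at two. A limit of 40% addresses the first only. A reader or an IRB that relies on Section 7.4 would credit the design with more protection than the cap gives.

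Site matters for this endpoint. The outcome is whether a lesion received adjunctive treatment, and Section 9.3 leaves that to the physician's judgement of the patient's interest. No blinding of the operator is described. The threshold for adding a device may therefore differ between sites. If two sites supply most patients, the observed rates and their difference largely describe practice at those two sites.

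The analysis does not make up for this. It drops a factor within which patients were randomised, and it leaves open whether by-site results will be shown. At stake are generalisability, a small loss of efficiency in the primary test, and the visibility of any difference in effect between sites.

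**Working it through.** **Inputs.** From Section 11.1: cap of 80 patients or 40%; about 200 patients; stop at 250 lesions or more; 40% of patients with a second lesion; adjunctive rates of 5% and 15%; 125 lesions per group. From Section 11.3.1: one-sided Z-test at 0.05.

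**1. The plan's own figure.** 0.40 × 200 = 80, so the two forms of the cap agree at 200 patients.

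**2. What the cap allows at 200 patients.**
- One site: 80/200 = 40%, below half. A one-site majority is prevented.
- Two sites: 2 × 80 = 160, and 160/200 = 80%. A two-site majority is allowed.
- Three sites could complete the trial, since 200/80 = 2.5.
- For any two sites to hold no more than half, the cap would have to be 50%/2 = 25%, or 50 of 200.

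**3. If the total is not 200.** Section 11.1 does not say which form of the cap then governs. With 1.4 lesions per patient, 250 lesions are reached at 250/1.4 = 178.6, about 179 patients. A total of 220 is included to show the other direction.

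| Total patients | 40% limit, two sites | 80-patient limit, two sites |
|---|---|---|
| 179 | 2 × 71 = 142 (79%) | 160 (89%) |
| 200 | 160 (80%) | 160 (80%) |
| 220 | 2 × 88 = 176 (80%) | 160 (73%) |

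The 89% entry puts 80/179 = 44.7% of patients at each site, which breaks the 40% limit in the same sentence. It should not be used as the headline. Every reading allows a two-site majority.

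**4. Effect of leaving site out.** Assume, for illustration, three sites with 40%, 40% and 20% of lesions, adjunctive rates of 30%, 5% and 5%, exact 1:1 balance within site, independent lesions and no treatment effect.
- Overall rate: 0.4 × 0.30 + 0.4 × 0.05 + 0.2 × 0.05 = 0.15.
- Variance per lesion used by the pooled Z-test: 0.15 × 0.85 = 0.1275.
- Actual variance within sites: 0.4 × 0.21 + 0.4 × 0.0475 + 0.2 × 0.0475 = 0.1125.
- The Z statistic then has standard deviation √(0.1125/0.1275) = 0.939. The effective cut-off is 1.645/0.939 = 1.75, a one-sided tail of 4.0%.

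Simulation agrees: the unadjusted test rejects about 4.0% of the time, against 4.8% when all sites share one rate. A site-stratified Mantel-Haenszel test rejects about 5.1% in the unequal-rate case.

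**5. Power.** With the same shares and control rates, and Enforcer rates one third as large (averages of 15% and 5%, as planned), power is about 87% unadjusted and about 88% stratified. With ten equal sites and one common rate per arm, it is about 85.5% unadjusted and 85.4% stratified. Stratifying gains a little when sites differ and costs almost nothing when they do not.

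**6. How finely to stratify.** Expected events are 125 × 0.05 + 125 × 0.15 = 25. Ten sites crossed with the two other randomisation factors give 10 × 2 × 2 = 40 cells, or 25/40 = 0.6 events per cell. That is too sparse, so stratification should be by site without the full cross.

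**The case against.** The strongest reply is that Section 7.4 promises only to reduce bias and never says that a two-site majority cannot occur. The cap does prevent a majority at one site and stops two sites from supplying the whole trial. That stands, and it rules out saying that the cap does nothing. The mismatch remains: the situation that the section names is still allowed, up to about 80%.

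A second reply is that randomisation within site balances site practice between the arms. This also stands. A reader might infer that concentration at two sites biases the comparison or inflates the type I error. The documents do not support that, and in the illustration the error goes the other way, with a conservative test.

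Third, Section 11.5 plans an examination across sites, so site is not ignored altogether. The gap is narrower: site is outside the primary analysis, and reporting is conditional with no criterion.

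Fourth, replacing the primary test is more than a change of words. With about 25 events, a pooling rule chosen after seeing the data would itself be a weakness. This is why the rule has to be fixed in advance and the full cross avoided.

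Finally, stratifying by site does not remove any tendency of unblinded operators to treat the two arms differently. Such a tendency would persist within each site and is a separate matter.

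**Conclusion.** The point holds in a limited form. The cap serves the one-site half of its stated purpose and not the two-site half. Two sites may supply 80% of patients at the planned 200, or about 79% if the 40% limit is applied at about 179. A figure near 90% needs the 80-patient limit to override the 40% limit, and the plan does not say that it does.

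The consequence is limited generalisability, not a confounded comparison. Leaving site out makes the primary test somewhat conservative if site rates differ: 4.0% instead of a nominal 5%, with about one percentage point of power lost in the illustration. Those two figures rest on assumed site rates of 30%, 5% and 5%, exact balance within site, and lesions independent as Section 11.1 assumes. The shares in step 2 rest on the plan's own numbers alone. The 179-patient total also assumes the plan's 40% second-lesion rate and stopping at 250 lesions.

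**What to change.** - **Section 11.3.1 and 11.5:** make the primary estimate and test a Mantel-Haenszel risk difference stratified by site. State the variance estimator and the rule for pooling small sites before any outcome data are seen. Do not cross site fully with lesion number and access type. Keep the unadjusted Z-test as a supporting analysis.
- **Section 11.5:** report the primary endpoint by site and arm in all cases.
- **Section 7.4:** say that the cap prevents a majority at any single site.
- **Section 11.1:** say whether the 80-patient or the 40% limit governs when the total differs from 200.

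The cost is a pre-specified pooling rule, a short power check for the stratified test, and slightly more analysis work. No patients or procedures are added. A cap of 25% or less would meet the two-site purpose as now written, but it could slow enrolment and is optional.

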7.4.1 Randomization

Once baseline angiography is complete and patient eligibility is confirmed, patients will be randomized into either the Enforcer balloon or conventional angioplasty group prior to treatment. At each study site, patients will be stratified for randomization based on the number of lesions requiring treatment (single lesion or two lesions) and type of AV access circuit (fistula or graft), then randomized to one of the treatment groups in a 1:1 ratio.

7.5 Endpoints

7.5.1 Primary Endpoint

The primary endpoint is the percentage of lesions receiving adjunctive treatment immediately following the study procedure (initial treatment with the Enforcer or conventional angioplasty balloon).

7.5.2 Secondary Endpoints

- Numeric rating scale (NRS) for pain experienced during study procedure balloon inflations
- Procedural cost
- Procedure times
- Maximum balloon pressure
- Device success
- Safety measures, including rupture, circumferential tears, and reintervention/patency

7.5.3 Additional Measures

- Anatomic success
- Clinical success
- Adverse events (refer to Section 9.6: Adverse Events for a list of reportable events)
- Primary patency through 90 days

7.5.4 Rationale for Endpoint and Additional Measures

The primary endpoint was chosen as it allows for the direct comparison of the rates of adjunctive treatment between the Enforcer balloon and other commercially available standard angioplasty balloons. The secondary endpoints and additional measures were chosen as applicable indicators of device effectiveness because of their similarity to those of interest in the literature and their similarity to other clinical studies.

7.6 Variables to be Measured to Demonstrate Achievement of Endpoints

The endpoints and additional measures will be assessed as described in Table 7.6-1.

Table 7.6-1. Assessment of Endpoints and Measures

Endpoint/Measure	Measure/Assessment
Use of adjunctive therapies	Procedural use of high-pressure balloons, cutting balloons, or stents following the study procedure (initial treatment with Enforcer or conventional angioplasty balloon)
Device success	Residual stenosis less than 30% within the treated lesion immediately after angioplasty with the study device (Enforcer or conventional angioplasty balloon)
Anatomic success	Residual stenosis less than 30% within the treated lesion following procedure (including any adjunctive therapy)
Procedural costs	Procedural charges and cost-to-charge ratio assessed after submission of UB-04 or CMS-1500 forms
Procedural time	Procedural time (defined as the time from needle entry for intervention to sheath withdrawal) will be assessed after angioplasty with the study device (Enforcer or conventional angioplasty balloon)
Balloon pressure	Maximum inflation pressure and duration
Numeric rating scale (NRS) for pain experienced during study procedure balloon inflations	Patient-reported pain assessment (scale of 0-10, where 0 indicates no pain and 10 indicates the worst possible pain)
Clinical success	Resumption of successful hemodialysis for at least one session from chart review through 90 days
Primary Patency	Uninterrupted patency of the AV hemodialysis access circuit assessed by reporting of reintervention or abandonment of dialysis

	access circuit from chart review through 90 days
Adverse events	Event information from chart review through 90 days 
Refer to Section 9.6: Adverse Events, for a list of reportable events

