1.0 Study Plan Overview

Objective:	To evaluate the necessity of adjunctive therapy following treatment of stenoses of a mature native arteriovenous (AV) dialysis access circuit fistula or graft with the Advance® Enforcer™ 35 Focal-Force PTA Balloon Catheter (hereafter referred to as the Enforcer balloon) compared to stenoses initially treated with commercially available conventional balloon angioplasty.
Design of the clinical study:	Multicenter, stratified, randomized, controlled clinical study
Primary endpoint:	The primary endpoint is the percentage of lesions requiring adjunctive treatment immediately following the study procedure.
Number of patients:	Approximately 200 patients (at minimum 250 lesions)
Number of clinical sites:	Up to 10 clinical sites
Patient participation duration:	Patient's medical records will be reviewed through 90 days post-procedure.
Expected study duration:	Patient enrollment is expected to be completed within 1 year of study initiation. Total study duration (from study initiation through patient enrollment and follow-up) is expected to be 15 months.

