8.0 Eligibility Criteria

Patient eligibility for enrollment will be based on existing information at the time of the procedure. Information obtained at a later date may contradict these criteria, but this will not be considered a deviation from the study plan.

Inclusion Criteria

A patient is suitable for inclusion in the study if the patient meets the following criteria:

1. A greater than 50% stenosis (when compared to the reference vessel diameter) of a mature native AV dialysis access circuit fistula or graft in the upper extremity³
2. Clinical or physiological abnormalities which indicate dialysis access dysfunction (e.g., decreased access blood flow, elevated venous pressure, decreased dialysis dose, abnormal physical exam)

Exclusion Criteria

Patients must be excluded from enrollment into the study if any of the following are true:

General Exclusion Criteria:

1. Less than 18 years old
2. Unwilling or unable to provide informed consent
3. Unwilling or unable to comply with the study schedule
4. Pregnant, lactating, or planning to become pregnant in the 3 months following enrollment
5. Simultaneously participating in an investigational drug or device study involving treatment of the AV dialysis access circuit in which the follow-up phase for that study's primary endpoint has not been completed 30 days or more prior to being enrolled in this study

Medical Exclusion Criteria:

6. Underwent any surgical or interventional procedure of the access circuit less than or equal to 30 days prior to the enrollment

7. Medical condition or comorbid conditions that would limit life expectancy to less than 6 months
8. Scheduled for a kidney transplant
9. Evidence of systemic or local infection associated with the AV dialysis access circuit
10. Uncorrectable bleeding diathesis or coagulopathy or will refuse blood transfusions
11. Stent or stent graft in or directly adjacent to the study lesion

Anatomic Exclusion Criteria:

12. Untreated hemodynamically significant central venous stenosis (>50%); (Central venous stenosis may be treated per standard of care during the study procedure)
13. Inability to cross a study lesion with a guidewire
14. Study lesion is greater than 4 cm in length (maximum of 4 cm per lesion and 8 cm total, if two lesions are treated)
15. Reference vessel diameter is less than 6 mm or greater than 10 mm
16. Presence of more than two distinct lesions (stenoses) in the AV dialysis access circuit

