9.2 Point of Enrollment

Patients are considered enrolled in the study once the balloon catheter is first introduced into the patient's body.

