11.4 Missing Data

For the primary endpoint, minimal or no missing data is expected. Missing primary outcome will be assumed missing at random and excluded for analyses. However, if more than 5% of primary endpoint is missing, multiple imputation technique will be applied followed by sensitivity analyses. All the other measurements will be analyzed accordingly with all available data using a complete case approach.

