APPENDIX D Definitions

Adjunctive Therapy: Additional treatment necessary for achievement of clinical success immediately following treatment with the study device (Enforcer balloon) or control device (conventional balloon angioplasty). Adjunctive therapies may include high-pressure balloon angioplasty, cutting balloon angioplasty, stents or stent graft.

Adverse Event: Any untoward medical occurrence, unintended disease or injury, or untoward clinical signs (including abnormal laboratory findings) in patients, users, or other persons, whether or not related to the investigational medical device. Refer to Section 9.6: Adverse Events for a list of reportable events.

Anatomic Success: Residual stenosis less than 30% within the treated lesion following the study procedure (including adjunctive therapy).

Arteriovenous (AV) Hemodialysis Access Circuit (also Access Circuit, Dialysis Access Circuit):

- AV Fistula - The vascular conduit beginning from the arterial inflow (2 cm upstream from the AV anastomosis) and ending at the confluence of the cephalic and axillary veins.
- Graft – The vascular conduit beginning from the arterial inflow (2 cm upstream from the artery-graft anastomosis) and ending at the confluence of the cephalic and axillary veins.

AV Hemodialysis Access Circuit, Mature: Native fistula has been successfully used for at least one hemodialysis treatment. Grafts included in the study will have also been successfully used for at least one hemodialysis treatment.

Clinical or physiological abnormalities which indicate dialysis access dysfunction:

Abnormalities may include the following:

- Decreased access blood flow (e.g., <600ml/min, decrease in flow)
- Elevated venous pressure
- Decreased dialysis dose (Kt/V)
- Abnormal physical exam

Clinical Success: Resumption of normal dialysis for at least one session.

Conventional Angioplasty Balloon: A balloon catheter having a rated burst pressure less than 25 atmospheres.

Device Deficiency: Inadequacy of a medical device with respect to its identity, quality, durability, reliability, safety, or performance.

Device Success: Residual stenosis less than 30% within the treated lesion immediately after angioplasty with the study device (Enforcer or conventional angioplasty balloon).

Dissection: Linear filling defect due to disruption of the intima, staining within the vessel wall.

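### The primary event counts only adjunctive devices used after the assigned balloon, so a randomised lesion that the balloon could not reach, or that received such a device first or instead, has no clear score

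*Combined protocol and SAP*

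**What the plan says.** The primary event is stated in four places, and all four set the same order in time.

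- Section 1.0: "The primary endpoint is the percentage of lesions requiring adjunctive treatment immediately following the study procedure".
- Section 7.5.1: "The primary endpoint is the percentage of lesions receiving adjunctive treatment immediately following the study procedure".
- Table 7.6-1 in section 7.6: "Procedural use of high-pressure balloons, cutting balloons, or stents following the study procedure (initial treatment with Enforcer or conventional angioplasty balloon".
- Appendix D, under adjunctive therapy: "Additional treatment necessary for achievement of clinical success immediately following treatment with the study device", or with the control device.

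Other sections decide which lesions reach the analysis.

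- Section 7.4.1 places randomisation after baseline angiography and before treatment.
- Section 8.0 has one exclusion about crossing the lesion: "Inability to cross a study lesion with a guidewire". It does not cover whether a balloon catheter can be delivered.
- Section 9.2: "Patients are considered enrolled in the study once the balloon catheter is first introduced into the patient's body".
- Section 11.3.1 compares lesions treated with each device. No intention-to-treat or other analysis set is defined.
- Section 11.4: "Missing primary outcome will be assumed missing at random and excluded for analyses". Multiple imputation with sensitivity analyses applies only if more than 5% of primary outcomes are missing.

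Section 9.3 describes the expected course: the assigned balloon, completion angiography, then any adjunctive procedure. Section 9.1 allows pre-treatment, but only of thrombosed circuits and central venous lesions. No section covers a study lesion that is prepared with another device first, cannot be reached by the assigned balloon, or is treated with something else instead.

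**The concern.** The objective in section 3.0 is how often each balloon has to be supplemented. A lesion that the assigned balloon cannot reach, or that receives a high-pressure balloon, cutting balloon or stent in its place, is plain evidence that the balloon was not enough. Yet the event depends on the adjunctive device coming second.

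Guidewire crossing is the only delivery test before allocation, so failed delivery of the balloon can come to light only after randomisation. If the loss falls mainly in the Enforcer arm, that arm's event rate is too low and a false claim of superiority becomes more likely. If it falls mainly in the control arm, true control events disappear and power drops. The plan describes no blinding, and section 7.4 relies on uniform endpoint definitions to limit bias, so a gap in the definition of the primary event matters.

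**Working it through.** **Inputs.** From section 11.1: rates of 5% (Enforcer) and 15% (conventional), 125 lesions per group, 80% power, type I error 0.05, lesions independent. From section 11.3.1: one-sided Z-test, p < 0.05. The share of lesions affected is not in the documents; 1 to 5 percentage points is assumed.

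**The plan's own figure.** Section 11.1 does not name its method. The pooled normal formula, n = [1.645·√(2·p̄(1−p̄)) + 0.842·√(p1(1−p1) + p2(1−p2))]² / (p2−p1)², with p̄ = 0.10, gives (0.698 + 0.352)² / 0.01 = 110.2, so 111 per group. A one-sided Fisher exact test has power 79.8% at 125 and 80.1% at 126, which matches the stated 125. The planned uncorrected Z-test at 125 per group has exact power 86.2%.

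**What the wording does to each kind of lesion.**

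| What happens in the study lesion | Result on the literal wording |
|---|---|
| Assigned balloon inflated, listed device used afterwards | Event |
| Listed device used first, then the assigned balloon | Non-event: the device did not follow |
| Assigned balloon never introduced, listed device used instead | Not treated with the assigned device; if no balloon catheter was introduced at all, randomised but not enrolled under 9.2 |
| Assigned balloon introduced but not deliverable, listed device used instead | Unsettled: an event if the attempt counts as initial treatment, otherwise a non-event or excluded |

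**How few lesions matter.** Expected events are 0.05 × 125 = 6.25 and 0.15 × 125 = 18.75, about 6 and 19. The test is Z = (pC − pE) / √[p̄(1−p̄)(1/nE + 1/nC)].

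- 6/125 vs 19/125: p̄ = 0.100, SE = 0.0379, Z = 0.104/0.0379 = 2.74, one-sided p = 0.003.
- Three more Enforcer events, 9/125 vs 19/125: Z = 2.01, p = 0.022.
- Five more, 11/125 vs 19/125: Z = 0.064/0.0411 = 1.56, p = 0.060.
- The same five lesions dropped, 6/120 vs 19/125: Z = 0.102/0.0387 = 2.64, p = 0.004.

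Five uncounted Enforcer lesions (4%) would therefore separate a significant result from a non-significant one, and dropping them conceals this as well as scoring them as non-events does.

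**Operating characteristics** (exact binomial enumeration, 125 per arm, one-sided 0.05):

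| Truth | Uncounted | Chance of claiming superiority |
|---|---|---|
| 15% vs 15% | none | 5.0% |
| 15% vs 15% | 2 points, Enforcer only | 11.6% |
| 15% vs 15% | 3 points, Enforcer only | 17.0% |
| 15% vs 15% | 2 points, both arms | 5.0% |
| 15% vs 15% | 3 points, both arms | 5.1% |
| 5% vs 15% | none | 86.2% |
| 5% vs 15% | 2 points, control only | 73.7% |
| 5% vs 15% | 3 points, control only | 65.4% |
| 5% vs 15% | 1 point, both arms | 89.5% |
| 5% vs 15% | 2 points, both arms | 92.8% |

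The harm comes from a difference between arms. Equal loss leaves the error rate alone and does not reduce power.

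**The case against.** Much of the case on the other side is sound.

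- A reader might infer that the plan has a rule scoring these lesions as non-events or dropping them. It states no such rule; that result follows from the literal wording. A site could read a failed attempt as initial treatment and count the replacement device. This narrows the point to an unspecified score, but scoring that can differ between sites is still a weakness in a primary endpoint.
- A reader might infer that a balloon that is inflated but does not open the lesion escapes the count. It does not: initial treatment has been given, and a listed device used next is an event.
- A reader might infer that the operator is free to choose the device order. Section 9.3 and Table 9.3-1 call for the assigned balloon first, and section 12.0 bars non-emergency departures without prior approval and requires them to be reported. Using a listed device first or instead is thus a deviation. Reporting a deviation does not score the lesion, however.
- Section 11.4 does not plainly apply where another device was used, because section 9.3 has additional procedures documented, and imputation is planned above 5% missing. But 5% is about 6 of 125 lesions per arm, or 12.5 of 250 overall, so losses of the size that matter can stay below the trigger. An outcome absent because the device failed is also not missing at random.
- The p = 0.060 example adds 5 hidden failures to 6 observed ones, so nearly half of all Enforcer failures would have to be of this kind. It shows sensitivity and is not a forecast.

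**Conclusion.** The point holds in a limited form. As written, a randomised study lesion to which the assigned balloon could not be delivered, or which received a listed adjunctive device before or instead of it, is not clearly an event and on the literal wording leaves the count. That omission can be read directly from the text; its frequency cannot.

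The documents do not support the stronger conclusion that the trial is biased in favour of Enforcer. Neither the size nor the direction of any loss is known. The rise in one-sided error from 5% to about 12-17% assumes 2 to 3 points lost in the Enforcer arm alone, equal true need of 15%, and independent lesions. With equal loss in both arms the error stays near 5%. What justifies action is that about 6 Enforcer events are expected, so a handful of lesions could change the result, and that the rule can be settled cheaply before outcomes are seen. This is a change that should be made, not one on which the trial's validity has been shown to depend.

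**What to change.** 1. In sections 1.0 and 7.5.1, Table 7.6-1 and Appendix D, change only the timing: the event is use of a listed adjunctive device in a study lesion at any time from randomisation to sheath withdrawal, whether before, instead of or after the assigned balloon.
2. Keep the plan's own device list and make it the same everywhere. Table 7.6-1 names stents, while section 9.3 and Appendix D also name stent grafts. Do not widen the list to any device other than the assigned type: an ordinary conventional balloon would then be an event in the Enforcer arm, while a second one in the control arm would not.
3. State in sections 11.3.1 and 11.4 that all randomised study lesions are analysed in the assigned arm, and that a lesion to which the assigned balloon could not be delivered is an event and not a missing value. Limit this to failed delivery. Scoring inadequate dilation by itself as an event would mix the endpoint with device success: in the earlier single-arm study in section 5.0, 39 − 25 = 14 of 39 lesions missed the residual-stenosis target, but only one needed adjunctive treatment.
4. Record device order per lesion on the eCRF.

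The cost is wording in four definitions and two analysis sections, plus one eCRF field. Care does not change. Observed event rates may be slightly less favourable, and the sponsor should check the sample size against that. If such lesions add 1, 2 or 3 points to the Enforcer rate only, exact power at 125 per group falls from 86% to 77%, 66% or 54%, and the pooled formula gives 143, 189 or 256 lesions per group for 80% power, against 111 with none. These shares are assumptions, and equal additions in both arms would cost less.
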